## 9.5 Analysis Populations

Analyses will be conducted on the complete dataset.

The data of the subjects who do not satisfy both of the following conditions will be excluded:

- During the initial 'intense' 2 weeks, the participant performed a minimum of 20% of the target complex impedance and TIM measurements.
- After the initial 'intense' 2 weeks, the participant performed a minimum of 10% of the target complex impedance and TIM measurements.

[REDACTED]

## 9.6 Endpoint Analyses

### 9.6.1 Primary Endpoint Analyses

The primary objectives will be assessed by using descriptive statistics such as means, SD, confidence intervals.

[REDACTED]

## 9.7 Safety Analyses

There is no formal statistical hypothesis. Adverse events will be tabulated according to the study interval, the

number of procedure-related events, and the number of device-related events. Procedure- and device-related adverse events will be summarized as rates, where the numerator for each rate will be the number of subjects with at least one procedure- or device-related event, and the denominator will be the total number of subjects. Adverse events will be reported by type, frequency, and severity. No formal statistical comparisons will be conducted.

## 9.8 Interim Analyses

No formal interim analysis will be conducted. However, given the feasibility nature of the study, it is planned to monitor findings continuously to inform modifications to the research tool and/or study procedures when required and to continuously inform the development of the research tool.

## 10 INFORMED CONSENT PROCESS

The Investigator shall obtain written informed consent from the subject using an approved Informed Consent Form (ICF) prior to any clinical investigation-related examination or activity. The rationale of the clinical investigation, as well as the benefits and risks, what participation will involve, and established alternatives to participation will be explained to the subject in native non-technical language, understandable to the subject. Ample time will be provided for the subject to enquire about details of the clinical investigation and to decide whether to participate.

All questions about the clinical investigation shall be answered to the satisfaction of the subject. Subjects shall not be coerced or unduly influenced to participate or to continue to participate in a clinical investigation. They shall not waive or appear to waive their legal rights.

Each subject and the person who conducted the informed consent discussion, shall sign and personally date the ICF. Where required, an independent and impartial witness shall sign and personally date the ICF. A copy of the signed ICF shall be given to the subject. The original signed ICF shall be archived in the Investigator's Site File or subject file at the investigational site.

This process shall be documented in the subject's source documents.

The subject shall be informed in a timely manner if new information becomes available that may be relevant to the subject's willingness to continue participation in the clinical investigation. The communication of this information must be documented as an update to the ICF and re-consent of the subject.

## 11 ADVERSE EVENTS AND DEVICE DEFICIENCIES

### 11.1 Definitions

#### 11.1.1 Adverse Event

An adverse event (AE) is any untoward medical occurrence, unintended disease or injury, or untoward clinical signs (including abnormal laboratory findings) in subjects, users or other persons whether or not related to the research tool or the procedures required for implant or use, and whether anticipated or unanticipated.

NOTE 1: This definition includes events related to the research tool or the comparator device.

NOTE 2: This definition includes events related to the procedures involved.

NOTE 3: For users and other persons, this definition is restricted to events related to the use of research tools.

### **11.1.2 Adverse Device Effect**

An adverse device effect (ADE) is an AE related to the use of a research tool.

NOTE 1: This includes any AE resulting from insufficiencies or inadequacies in the instructions for use, the deployment, the implantation, the installation, the operation, or any malfunction of the research tool.

NOTE 2: This definition includes any event resulting from use error or from intentional misuse of the research tool.

NOTE 3: This includes 'comparator' if the comparator is a research tool.

### **11.1.3 Serious Adverse Event**

A serious adverse event (SAE) is any AE that led to any of the following:

- 1) death,
- 2) serious deterioration in the health of the subject, users, or other persons as defined by one or more of the following:
  - a life-threatening illness or injury, or
  - a permanent impairment of, or damage to, a body structure or a body function including chronic diseases, or
  - in-patient hospitalisation or prolonged hospitalisation, or
  - medical or surgical intervention to prevent life-threatening illness or injury or permanent impairment or damage to a body structure or a body function,
- 3) foetal distress, foetal death or a congenital physical or mental abnormality, or birth defect including physical or mental impairment.

NOTE: Planned hospitalisation for a pre-existing condition, or a procedure required by the CIP, without serious deterioration in health, is not considered a SAE.

### **11.1.4 Serious Adverse Device Effect**

A serious adverse device effect (SADE) is an ADE that has resulted in any of the consequences characteristic of a SAE.

### **11.1.5 Unanticipated Serious Adverse Device Effect**

An unanticipated serious adverse device effect (USADE) is a SADE, which by its nature, incidence, severity, or outcome has not been identified in the current version of the hazard analysis, IB, IFU, CIP or ICF.

NOTE: An anticipated serious adverse device effect is an effect, which by its nature, incidence, severity, or outcome has been identified in the hazard analysis, IB, IFUs, CIP or ICF.

### **11.1.6 Adverse Events of Special Interest**

Not applicable

### 11.1.7 Device Deficiency

A Device Deficiency (DD) is an inadequacy of a research tool with respect to its identity, quality, durability, reliability, usability, safety, or performance.

NOTE 1: Device Deficiencies include malfunctions, use errors, and inadequacy in the information supplied by the manufacturer including labelling.

NOTE 2: This definition includes device deficiencies related to the research tool or the comparator.

### 11.1.8 Serious Health Threat

A signal from any adverse event or device deficiency that indicates an imminent risk of death or a serious deterioration in the health in subjects, users or other persons, and that requires prompt remedial action for other subjects, users or other persons.

NOTE: This would include events that are of significant and unexpected nature such that they become alarming as a potential serious health hazard or possibility of multiple deaths occurring at short intervals.

## 11.2 Recording and Handling of Adverse Events

Subjects shall be carefully monitored during the clinical investigation and the investigator should enquire about AEs at investigation visits.

All AEs will be recorded from the time of contact with the research tool. AE recording will continue for each subject until completion of their End of Study visit. Ongoing SAEs and SADEs will be followed for 30 days, or until resolution or stabilisation of the event, whichever comes first.

Source notes should indicate the evaluation for AEs, even if there was none to report. All required AEs will be reported if observed, even if anticipated and/or acknowledged as a risk factor in the consent.

All AEs will have the following information documented: start and stop dates, action taken, outcome, severity and investigators opinion on the potential relationship to the research tool and study procedures. If an AE changes in severity, the most severe (highest) grade will be captured for that event on the Adverse Events CRF.

### 11.2.1 Assessment of Severity

The Principal Investigator (or qualified delegate) will make an assessment of severity for each event based on clinical judgement. The intensity of each event recorded in the CRF should be assigned to one of the following categories:

Mild	An event that is easily tolerated by the subject, causing minimal discomfort and not interfering with everyday activities.
Moderate	An event that is sufficiently discomforting to interfere with normal activities
Severe	An event which is incapacitating and prevents normal everyday activities

### 11.2.2 Assessment of Causality

The Investigator will assess the potential causal relationship of each event, using clinical judgement. Alternative causes, such as natural history of underlying diseases, other risk factors and the temporal

relationship of the event to the research tool product will be considered and investigated. The causal relationship to the research tool is to be assessed by the Investigator (or medically qualified delegate) and should be assessed using the following classifications:

Not related	
Relationship to the medical device or procedures can be excluded when:
 
 
• the event is not a known side effect of the product category the device belongs to or of similar devices and procedures;
 
• the event has no temporal relationship with the use of the device or the procedures;
 
• the event does not follow a known response pattern to the medical device (if the response pattern is previously known) and is biologically implausible;
 
• the discontinuation of medical device application or the reduction of the level of activation/exposure - when clinically feasible - and reintroduction of its use (or increase of the level of activation/exposure), do not impact on the event;
 
• the event involves a body-site or an organ not expected to be affected by the device or procedure;
 
• the event can be attributed to another cause (for example, an underlying or concurrent illness/ clinical condition, an effect of another device, drug, treatment or other risk factors);
 
• the event does not depend on a false result given by the investigational medical device used for diagnosis, when applicable;
 
• harms to the subject are not clearly due to use error;
 
 
In order to establish the non-relatedness, not all the criteria listed above might be met at the same time, depending on the type of device/procedures and the event.

Unlikely related	The relationship with the use of the medical device seems not relevant and/or the event can be reasonably explained by another cause, but additional information may be obtained.
Possibly related	The relationship with the use of the medical device is weak but cannot be ruled out completely. Alternative causes are also possible (for example, an underlying or concurrent illness/ clinical condition or/and an effect of another device, drug or treatment). Cases where relatedness cannot be assessed or no information has been obtained should also be classified as possibly related.
Probably related	The relationship with the use of the medical device seems relevant and/or the event cannot be reasonably explained by another cause, but additional information may be obtained.
Definitely related	
The event is associated with the medical device or with procedures beyond reasonable doubt when:
 
 
• the event is a known side effect of the product category the device belongs to or of similar devices and procedures;
 
• the event has a temporal relationship with the medical device use/application or procedures;
 
• the event involves a body-site or organ that           
 
– the medical device or procedures are applied to
 
– the medical device or procedures have an effect on;
 
 
 
• the event follows a known response pattern to the medical device (if the response pattern is previously known);
 

	
 
the discontinuation of medical device application (or reduction of the level of activation/exposure) and reintroduction of its use (or increase of the level of activation/exposure), impact on the event (when clinically feasible);
 
other possible causes (for example, an underlying or concurrent illness/ clinical condition or/and an effect of another device, drug or treatment) have been adequately ruled out;
 
harm to the subject is due to error in use;
 
the event depends on a false result given by the medical device used for diagnosis, when applicable;
 
 
In order to establish the relatedness, not all the criteria listed above might be met at the same time, depending on the type of device/procedures and the event.

--	---------------------------------------------------------------------------------------------------------------------------------------------------------------------------------------------------------------------------------------------------------------------------------------------------------------------------------------------------------------------------------------------------------------------------------------------------------------------------------------------------------------------------------------------------------------------------------------------------------------------------------------------------------------------------------------------------------------------------------------------------------------------------------------------------------------------------------

Due to the different causality reporting requirements in participating regions, the Sponsor will request causality assessments from investigators using the five categories described in the preceding table. Cochlear will report causality to competent authorities and ethics committees based on local regional requirements as described in Section 11.4.2.

### 11.2.3 Assessment of Seriousness

The Investigator will assess the seriousness of each event according to clinical judgement and the definition provided in section 11.1.3.

### 11.2.4 Assessment of Expectedness

An event should be considered unanticipated if the nature, severity, or frequency of that event is not consistent with the applicable safety reference information, such as the hazards analysis, IB, or Product Information/IFU if the product is approved for marketing.

For this clinical investigation the listed items in Section 8.2 and 8.3 of this CIP are anticipated ADEs.

Anticipated	An adverse device effect (ADE) which by its nature, incidence, severity, or outcome is consistent with the applicable safety reference information (for example, IB, IFU).
Unanticipated	An adverse device effect (ADE) which by its nature, incidence, severity, or outcome is not consistent with, or has not been identified in the applicable safety reference information (for example, IB, IFU).

### 11.2.5 Non-reportable Adverse Events

As determined by risk assessment by the Sponsor, this study is deemed as a low risk study. AEs that occur as a result of a planned procedure that is not related to hearing or to the study procedure e.g. in-patient hospital stay for hip replacement, will not be reported.

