## 8.2 Anticipated Adverse Device Effects

Residual risks have been assessed in accordance with Cochlear's Product Risk Management Procedure. Only the following residual risk is relevant for this study and is classified as medium risk:

- During the execution of measurements, some of the stimulation pulses may be perceived as uncomfortable or result in pain or non-auditory stimulation for a short period of time. The users will be informed that they have the option to use a stop button in the app or take off the coil from their head.

Risk mitigations have been identified and will be implemented to ensure the residual risk associated with the use of this tool is acceptable. The likelihood of these risks is estimated low enough to judge them acceptable in the scope of the intended use cases.

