## 11.4 Reporting Responsibilities

The Investigator is responsible for reporting all AEs and DDs in the CRF.

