### 11.4.1 Investigator Reporting of Serious Adverse Events

All AEs meeting the criteria for an SAE, or DD that could have led to an SADE must be reported to the Sponsor in accordance with timeframes required by local regulations, as follows:

Country	Timeframe
Australia	24 hours
Belgium	24 hours
Sweden	24 hours

Reporting is achieved through completion of the events details in the Adverse Event page of the eCRF.

The Investigator shall always provide an assessment of causality at the time of the initial report, as described in section 11.2.2 'Assessment of Causality'. If data obtained after reporting indicates that the assessment of causality is incorrect, then the SAE form may be appropriately amended, signed, dated, and resubmitted to the Sponsor.

If the Investigator does not have all other information regarding an SAE, he/she will not wait to receive additional information before reporting the event. The reporting forms shall be updated when additional information is received.

The Investigator is responsible for reporting of safety events to their local EC using the applicable report form, in accordance with local regulations. In Belgium/Sweden, reporting to the local EC is coincident with that to the Competent Authority.

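### The non-reportable-event rule in 11.2.5 has no limit by seriousness, so it conflicts with the 24-hour SAE reporting rule for serious complications of planned, unrelated procedures

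*Combined protocol and SAP*

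**What the plan says.** Section 11.2.5, on non-reportable events, covers "AEs that occur as a result of a planned procedure that is not related to hearing or to the study procedure". Its one example ends "in-patient hospital stay for hip replacement, will not be reported". The section does not mention seriousness and does not refer to 11.1.3, 11.4 or 11.4.1.

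Four other places bear on the same events:

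- **11.1.1** defines an AE "whether or not related to the research tool or the procedures required for implant or use", so an event does not leave the definition by being unrelated to the tool.
- **11.1.3** lists the SAE criteria, including death, life-threatening illness and "in-patient hospitalisation or prolonged hospitalisation". Its note says: "Planned hospitalisation for a pre-existing condition, or a procedure required by the CIP, without serious deterioration in health, is not considered a SAE".
- **11.4** states: "The Investigator is responsible for reporting all AEs and DDs in the CRF".
- **11.4.1** states: "All AEs meeting the criteria for an SAE, or DD that could have led to an SADE must be reported to the Sponsor". The table there gives 24 hours for each of the three countries. It adds that reporting is done by completing the Adverse Event page of the eCRF.

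Section 11.4.2 then commits the Sponsor to an expedited assessment of all SAEs. Section 9.7 tabulates adverse events by type, frequency and severity.

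**The concern.** The note in 11.1.3 and the rule in 11.2.5 look like two statements of one idea, but their scope differs. The note removes a planned admission from the SAE category, and only while the subject's health does not seriously worsen. Section 11.2.5 removes whatever adverse events follow from the planned procedure, and it has no such condition. The difference between the two is the set of serious complications.

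A site that applies 11.2.5 literally would keep such an event off the eCRF page through which 11.4.1 says SAEs are reported. The Sponsor would then have no SAE report to assess under 11.4.2. The site's own view that the event resulted from the unrelated procedure would have settled the matter before the five-category causality assessment in 11.2.2 was recorded. The event would also be absent from the tables in 9.7.

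**Working it through.** No calculation decides this point, and the plan states no figure to reproduce. The check is to take three events after a planned hip replacement (the plan's own example) and apply each section in turn.

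| Event | 11.1.3 | 11.4 (CRF) | 11.4.1 (Sponsor, 24 h) | 11.2.5 | Compatible? |
|---|---|---|---|---|---|
| Uneventful planned stay | Not an SAE, by the note | Arguably no AE to enter | Does not apply | Not reported | Yes |
| Non-serious complication | AE, not an SAE | Enter | Does not apply | Not reported | Only if 11.2.5 is an exception to 11.4 |
| Life-threatening complication, or a prolonged stay | SAE; the note does not cover serious worsening | Enter | Report | Not reported | No |

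Row by row:

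1. **Uneventful stay.** The note and 11.2.5 agree. This is the only case that the example in 11.2.5 describes.
2. **Non-serious complication.** Section 11.4 has no exception, but 11.2 speaks of reporting the AEs that are required, which implies that some are not. Section 11.2.5 can be read as naming those. The text is untidy but can be made consistent.
3. **Serious complication.** The event is an AE under 11.1.1 whatever its cause. It meets at least one SAE criterion, and the note no longer protects it. Section 11.4.1 then applies without qualification. Section 11.2.5 also applies, because the event resulted from a planned procedure unrelated to hearing or to the study. One section says report within 24 hours and the other says do not report. No section says which prevails.

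**Exposure.** The schedule of events sets 8 weeks per subject, give or take 14 days, and 50 subjects are planned. That is 50 × 8 = 400 subject-weeks, with a range of 50 × 6 = 300 to 50 × 10 = 500. Dividing by 52 gives about 7.7 subject-years (5.8 to 9.6). The documents give no rate of planned procedures or of their complications, so no expected count can be derived.

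**The case against.** The best defence is that 11.2.5 is a deliberate exception. It has its own heading, a specific rule normally limits a general one, and 11.2 allows for AEs that need not be reported. Its only example is the admission itself, so the authors probably meant to restate the note in 11.1.3. This is a fair account of intent, and it may well excuse non-serious events. It does not settle serious ones. The operative words describe events that result from the procedure, not the procedure or the stay. The condition about worsening health is missing, and nothing gives 11.2.5 priority over 11.4.1.

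It can also be said that little would be lost. Section 11.2 still asks for all AEs to be recorded, the daily well-being questionnaire is meant to capture adverse events (7.3.3), medication changes are updated in the CRF (7.3.3.1), death is a listed withdrawal reason (7.2.6), and monitors check the data (22.1). This stands in part: a death would probably reach the Sponsor by another route, so a reader should not infer that it would go unseen. None of these routes carries the 24-hour limit. The Sponsor's Safety Data Handling Plan, which is not among the documents, may say more, but it would not correct the text that sites follow.

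Three stronger readings are tempting and are not supported:

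- **That 11.2.5 changes what an SAE is.** It does not. It conflicts with the reporting rules and with the limit in the note, and leaves the definition alone.
- **That its low-risk justification contradicts 8.2**, which says "Only the following residual risk is relevant for this study and is classified as medium risk". Section 11.2.5 refers to the study as a whole, while 8.2 classifies one residual risk of the tool. The two can differ, and neither concerns complications of unrelated surgery.
- **That the exemption removes infections the study rationale names as causes of impedance change.** Section 4.3 names upper-respiratory infections, not infections after surgery.

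**Conclusion.** The conflict is real, and it is confined to complications of planned, unrelated procedures that meet the SAE criteria. For those events a site cannot follow both 11.2.5 and 11.4.1. For non-serious complications there is a looser tension with 11.4, which can be resolved by reading 11.2.5 as an exception.

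The size cannot be put as a number of events. With roughly 400 subject-weeks of follow-up there may be few or none. The descriptive impedance endpoint does not depend on it. What is at stake is whether the safety record is complete and whether the Sponsor receives SAEs in time to assess them. It should be corrected because the fault lies in the instruction that sites follow and the remedy is slight.

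The conclusion assumes that sites would apply 11.2.5 as worded. A site that took it as a restatement of the 11.1.3 note would report correctly, but nothing in the text tells it to.

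**What to change.** Reconcile 11.2.5 with 11.1.3, 11.4 and 11.4.1. Limit 11.2.5 to the planned procedure or hospital stay itself. Add that any complication or deterioration in health arising from it is recorded as an AE and, if it meets the SAE criteria, is reported under 11.4.1. A cross-reference from 11.4 and 11.4.1 to the narrowed rule would remove any doubt about which section governs.

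This is one sentence of new text and a small number of additional AE entries. It changes no assessment, endpoint or analysis, and if the intent was to mirror the 11.1.3 note it leaves the intended policy as it was.
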